As per the communication from the Food and Drug Administration (FDA) in Aug 2013, there are concerns that hypopigmentation of the skin and mucous membranes may occur with BACE1 inhibitory drugs. Although no such effects have been seen with elenbecestat (E2609) to date, assessments using standardized photography will be performed by a central reviewing dermatologist at regular intervals during the Core Study. During the OLE Phase, a dermatologic assessment will be performed by the investigator at every scheduled visit. Every assessment will specifically include evaluation of any areas of depigmentation or any rash. (revised per Amendment 07) Dermatological assessments will be supplemented with a specific question to subjects regarding skin changes at each visit. Any such changes could be referred to the central reviewing dermatologist, and to a local dermatologist if needed, for further evaluation. See [Section 9.5.1.5.8](#) and [Appendix 6](#) for further details. (revised per Amendment 07)

- Baseline and on-study blood will be taken and stored for all subjects during the Core Study and OLE Phase. (revised per Amendment 02 and 07) DNA samples and CSF samples (for all subjects who consent to CSF sample collection) will be taken and stored during the Core Study. (revised per Amendment 02 and 07) These samples may be tested in the event that a subject develops AEs that warrant further investigation (eg, if a subject develops a treatment-emergent infection) (see [Section 9.5.1.2.2](#) and [Appendix 6](#)). (revised per Amendment 07)
- Central reading of safety brain MRI assessments (including any MRI evidence of demyelination) will be performed at Screening, at approximately 6-month intervals during the Core Study Treatment Period, and at the final Follow-Up Visit during the Core Study. (revised per Amendment 07) MRI assessments will also be performed at the end of the OLE Treatment Period. In addition, safety brain MRI assessments may be performed as an unscheduled assessment if clinically indicated. (revised per Amendment 07)
- Full neurologic examinations will be performed at Baseline and at regular intervals during the study by either a neurologist or a physician with comparable training and experience in undertaking neurologic examinations. Details of the neurologic examination are given in [Section 9.5.1.5.9](#) and [Appendix 6](#). (revised per Amendment 07)

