9.5.1.5.8 DERMATOLOGIC ASSESSMENT

During the Core Study, centralized skin assessments, using standardized photography, will be performed by a reviewing dermatologist at the times shown in [Table 6](#) and [Table 7](#). During the OLE Phase, all dermatologic assessments will be performed by the investigator at the times shown in [Table 14](#). (revised per Amendment 07) All assessments will specifically include evaluation of any areas of depigmentation or any rash.

In addition, subjects will be questioned by the investigator at each visit about any new lesions on the skin, orolabial area, genital area, mucous membranes and conjunctiva, or visually detectable changes that might represent a drug-induced rash/reaction or infection. Subjects and their caregiver or informants will be instructed to contact the investigator promptly if they see any lesions or other symptoms that might be associated with a drug-induced rash or reaction, or infection, and the investigator will be required to review such AEs as soon as possible and consider an unscheduled physical and dermatological evaluation. Detailed characteristics of any skin rashes will be captured in the clinical database. Physical examination may be undertaken where indicated. Treatment-emergent abnormal dermatological findings should be reported as AEs.

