There will be no centralized dermatological assessments in the OLE Phase; however, dermatological assessments will be performed by the investigator at every scheduled visit and as needed, at an unscheduled visit. These assessments will specifically include evaluation of any areas of depigmentation or drug-induced vitiligo as well as any evidence of rash. Subjects will also be questioned by the investigator at each visit to identify any changes that might represent a drug-induced rash/reaction or infection. Subjects and their study partners will be instructed to contact the investigator if they see any lesions or other symptoms that might be associated with a drug-induced rash/reaction or infection, so that such AEs can be reviewed promptly.

Full neurologic examinations will be performed at the start of the OLE (Visit 20 or 21), and every 6 months during the OLE treatment period. An additional neurologic examination will also be performed at the final Follow-Up Visit. The neurologic examinations will include

muscle strength testing and assessment of cranial nerves including olfaction, with the use of the Brief Smell Identification Test, as well as other parts of the central nervous system (CNS).

Complete blood counts and percentages will be measured (by a centralized laboratory) every scheduled visit. Additional blood sample will be collected and stored at each scheduled visit; these samples may be used for exploratory biomarker analyses or be analyzed in the event that the subject develops treatment-emergent adverse events that warrant further investigation.

Peripheral blood mononuclear cells (PBMCs) will be collected every scheduled visit and posttreatment for exploratory immunomodulatory and immune-based analyses. These blood samples will be collected at every visit and stored in the event that the subject develops treatment-emergent adverse events that warrant further investigation (eg, treatment-emergent infection), these samples may be tested to determine whether the subject already had prior exposure to any suspected infective agents.

Safety brain MRI and vMRI assessments will be performed at the end of the OLE treatment period (Visit 32 or ED). Additional safety MRI scans are to be performed as clinically necessary. MRI acquisition and interpretation will be organized centrally to ensure reproducibility and consistency between units involved.

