- c: Blood samples for will be collected and stored. These samples may be used for exploratory biomarker analyses, or in the event that the subject develops treatment-emergent adverse events that warrant further investigation (eg, treatment-emergent infection), these samples may be tested to determine whether the subject already had prior exposure to any suspected infective agents.

STUDY DRUG SUPPLIES

Elenbecestat (E2609) tablets of 50-mg dose strengths will be supplied. Each subject will take 1 tablet per day.

SCHEDULE OF PROCEDURES/ASSESSMENTS

Table 14 presents the Schedule of Procedures/Assessments for the OLE Phase.

Table 14 Schedule of Procedures/Assessments in Study 202: Open-label Extension Phase

| Phase | Open-label Extension Phase | | | | | | | | | | | | | | | |
|---|----------------------------|----|----|----|----|-----|-----|-----|-----|-----|-----|-----|-----------------|------------------------|----------------|------------------------|
| | Treatment | | | | | | | | | | | | | Follow-Up ^d | | UNS Visit ^e |
| Period | 21 ^b | 22 | 23 | 24 | 25 | 26 | 27 | 28 | 29 | 30 | 31 | 32 | ED ^c | 33 | 34 | |
| Visit ^a | 1 | 2 | 3 | 4 | 5 | 6 | 7 | 8 | 9 | 10 | 11 | 12 | | 13 | 14 | |
| Day in OLE | 1 | 15 | 29 | 57 | 85 | 183 | 274 | 365 | 456 | 547 | 638 | 729 | | 757 | 813 | |
| Week in OLE | 1 | 3 | 5 | 9 | 13 | 27 | 40 | 53 | 66 | 79 | 92 | 105 | | 109 | 117 | |
| Weeks elapsed since 1st dose in OLE | 0 | 2 | 4 | 8 | 12 | 26 | 39 | 52 | 65 | 78 | 91 | 104 | | 108 | 116 | |
| Nominal months elapsed since first dose in OLE | 0 | | 1 | 2 | 3 | 6 | 9 | 12 | 15 | 18 | 21 | 24 | | 25 | 27 | |
| Procedures/ Assessments | | | | | | | | | | | | | | | | |
| Routine physical examination with dermatologic review | X ^{f,g} | X | X | X | X | X | X | X | X | X | X | X | X | X | X ^h | X |
| Inclusion and Exclusion criteria | X | | | | | | | | | | | | | | | |
| Vital signs, including respiratory rate ⁱ | X ^j | X | X | X | X | X | X | X | X | X | X | X | X | X | X ^h | X |
| Weight | X ^f | | | | | | | X | | | | X | X | | | X |
| Neurological examination ^k | X ^f | | | | | X | | X | | X | | X | X | | X | X |
| Concomitant medications ^l | X ^m | X | X | X | X | X | X | X | X | X | X | X | X | X | X | X |
| 12-lead ECG ⁿ | X ^f | | | | X | X | | X | | X | | X | X | X | X ^h | X |
| Clinical biochemistry and urinalysis | X ^j | X | X | X | X | X | X | X | X | X | X | X | X | X | X | X |

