- h: Only if clinically significant abnormalities are found at Visit 33 and the investigator considers it necessary to repeat at Visit 34.
- i: Measurements of body temperature and sitting blood pressure and sitting heart rate will be obtained.
- j: Result from Visit 20 will also serve as Visit 21 result if Visit 21 occurs within 10 days from Visit 20. If Visit 21 occurs more than 10 days after Visit 20, the assessment must be repeated at Visit 21.
- k: Examples of neurological signs that may indicate new central nervous system pathology that may need further investigation include (but not limited to) visual disturbance, dysarthria, dysphasia, muscle strength, limb weakness, hyperflexia, paraparesis, micturition difficulty or urgency or incontinence, ataxia, neuropsychiatric or cognitive decline in excess of expectations based on the subject’s recent history. The Brief Smell Identification Test (Sensonics Inc.) will be administered at the same visits and serves as part of the neurologic examination.
- l: Please refer to Section 9.4.7 which describes prohibited and permitted medications in the study.
- m: Result from Visit 20 will also serve as Visit 21 result if Visit 21 occurs on the same day as Visit 20. If Visit 21 occurs more than 1 days after Visit 20, the assessment must be repeated at Visit 21.
- n: Single 12-lead standard ECGs will be recorded. If the QTcF is greater than 450 ms, perform 2 more 12-lead standard ECGs 1 minute apart and take the mean of the 3 QTcF values.
- o: Reports of the lymphocyte subset analyses will be sent to the Sponsor only. Lymphocyte subsets will include but are not limited to the following cell surface marker assessments: CD4 [T helper cells], CD8 [cytotoxic T cells], CD19 [B cells], CD16/CD56 [NK cells] and CD14 [macrophages] and absolute lymphocytes. Regulatory T cells will also be measured. Viability staining may also be employed.
- p: PD blood samples should be collected at fasting or at least 2 hours after the most recent meal and, as far as is feasible, samples should be taken at the same time of day. All PD blood samples should be collected predose.
- q: If dipstick urinalysis performed at site is abnormal, a urine sample will be sent to the central laboratory for full urinalysis.

-

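### The text promises an investigator skin assessment at every scheduled OLE visit, but Table 14 footnote h makes it conditional at Visit 34, the last off-drug visit

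*Protocol*

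**What the plan says.** Three places in the protocol set the timing of skin assessment in the open-label extension (OLE).

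- Section 9.2.5 gives the rule: "During the OLE Phase, a dermatologic assessment will be performed by the investigator at every scheduled visit". It follows a statement that, after an FDA communication, "there are concerns that hypopigmentation of the skin and mucous membranes may occur with BACE1 inhibitory drugs".
- Appendix 6, under the extension phase assessments, drops the centralized photography used in the Core Study and states that "dermatological assessments will be performed by the investigator at every scheduled visit". The content is specified as "evaluation of any areas of depigmentation or drug-induced vitiligo as well as any evidence of rash".
- Section 9.5.1.5.8 refers the reader to the schedule: "During the OLE Phase, all dermatologic assessments will be performed by the investigator at the times shown in" Table 14.

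In Table 14 the only row covering the skin is "Routine physical examination with dermatologic review". Its Visit 34 cell carries footnote h: "Only if clinically significant abnormalities are found at Visit 33 and the investigator considers it necessary to repeat at Visit 34". Footnote d of the same table requires every OLE subject to attend Visits 33 and 34, whether or not treatment was completed.

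**The concern.** The prose has no exception and the schedule has one. For a subject with no abnormality at Visit 33, a site working from Section 9.2.5 or the body of Appendix 6 examines the skin at Visit 34. A site working from Table 14 does not. Both texts are current.

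At stake is the last scheduled look at the skin after the final OLE dose. With central photography discontinued, the investigator's examination is the only scheduled objective skin check in this phase. The phase has long-term safety as its primary objective, and the protocol itself links skin assessment to a concern about the drug class. If sites resolve the conflict differently, the final off-drug skin data will be uneven. If all follow Table 14, a check that the protocol promises twice will be left out for most subjects whose Visit 33 is normal.

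**Working it through.** There is no planned figure to reproduce. The check sets the text against the schedule, with a count of visits.

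**Locating the cell.** The skin row of Table 14 has 16 cells: Visits 21 to 32 (12 cells), early discontinuation, Visit 33, Visit 34 and unscheduled. Footnote h is on cell 15, which is Visit 34. The footnote also names Visit 34, so the reading does not depend on how the table was extracted.

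**Timing.** Nominal OLE days come from the header of Table 14: Visit 32 is Day 729, Visit 33 is Day 757 and Visit 34 is Day 813.

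- Visit 33: 757 − 729 = 28 days, or 4 weeks off drug.
- Visit 34: 813 − 729 = 84 days, or 12 weeks off drug. No later visit is scheduled.

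**Coverage.** Scheduled visits 21 to 34 number 14. Skin review is unconditional at 14 − 1 = 13 of them. Of the 2 off-drug visits, it is unconditional at 1 (Visit 33).

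**The condition.** Footnote h needs both a clinically significant abnormality at Visit 33 and the investigator's judgment that a repeat is necessary. A subject normal at Visit 33 fails the first part, so the schedule asks for no skin review at Visit 34. No other row of Table 14 supplies one.

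**Comparison with the Core Study.** Table 7 lists dermatology (central photography) in its own row, separate from the physical examination. Counting across that row, the cell for Visit 20, the 12-week off-drug visit, holds a mark with no condition. The repeat-only-if-abnormal wording in Table 7 is footnote e, which appears at Visit 20 on vital signs and ECG. The superscript on the physical examination was extracted as c and may be the same footnote. In the Core Study, then, the final skin check did not depend on the previous visit. In Table 14, where skin review shares a row with the physical examination, it does. That the condition was carried over by accident when the rows were merged is plausible, but it is an inference.

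**The case against.** The strongest reply is that the protocol already says which text governs. Section 9.2.5 is a risk-mitigation summary that refers onward to Section 9.5.1.5.8 and Appendix 6, and Section 9.5.1.5.8 hands timing to Table 14. The specific footnote would then override the general phrase. This reduces the ambiguity but does not remove it, because Appendix 6, which contains Table 14, restates the unconditional rule in its own text.

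A second reply is that references to every or each scheduled visit are used loosely in the OLE text. This is true:

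- Section 9.1.3 says it of vital signs, which also carry footnote h at Visit 34.
- Appendix 6 says it of the stored blood sample, for which Table 13 lists 8 time points rather than 14.
- Section 9.2.5 says it of the clinical suicidality assessment, which Table 14 leaves blank at Visit 21.

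Loose usage elsewhere makes an oversight more likely. It does not tell a site which skin instruction to follow.

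A third reply concerns consequence, and it largely stands. Visit 33 has an unconditional skin review. At every visit, "subjects will be questioned by the investigator at each visit about any new lesions on the skin", and the question extends to mucous membranes and conjunctiva. Subjects and their study partners are told to report lesions. Adverse events are collected through Visit 34, a neurological examination is scheduled there without condition, and unscheduled visits are available. Section 9.2.5 also records that no hypopigmentation had been seen with this drug. What is left uncovered is a change that nobody reports, in a population with cognitive impairment.

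Two stronger readings are tempting and should be resisted. A reader might infer that footnote g, which requires an investigator skin assessment at Visit 21, shows that the sponsor meant to protect the skin check throughout. It does not. Footnote f lets Visit 20 results stand in for Visit 21, and footnote g only prevents the Visit 20 photography from replacing the investigator's examination. A reader might also infer that off-drug surveillance for depigmentation has been abandoned. The unconditional review at Visit 33 and the safeguards just listed contradict that.

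**Conclusion.** The inconsistency is real and should be corrected, at low severity. It affects one short examination per OLE subject who is normal at Visit 33, at one of 14 scheduled visits and one of two off-drug visits. It rests on Table 14 as printed and on counting Visit 34 as a scheduled visit, which footnote d supports. The documents do not show which instruction was intended. The case for keeping the check is that the text promises it twice and the Core schedule had an unconditional counterpart at the same interval after dosing. The documents do not make any planned analysis, stopping rule or eligibility decision depend on this cell.

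**What to change.** Give dermatologic review its own row in Table 14, as Table 7 does, with an unconditional mark at Visit 34. Alternatively, keep the combined row and add a Visit 34 footnote stating that the skin review is exempt from footnote h. In either case leave footnote h as it is on the physical examination, vital signs and ECG.

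If the sponsor did intend to omit the check, amend the rule in Section 9.2.5 and in Appendix 6 so that both except Visit 34 on the same terms as footnote h.

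The cost is one table row or one footnote, plus a brief skin check at a visit that already takes place. The alternative costs two wording changes and no extra procedure.

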9.3 Selection of Study Population

Approximately 60 ($\pm 20\%$) eligible MCI/Prodromal or mild to moderate AD subjects will be randomized at approximately 35 sites in the United States (revised per Amendments 02 and 04). There will be no restriction to the number of subjects from either population.

Subjects who do not meet all of the inclusion criteria in [Section 9.3.1](#) or who meet any of the exclusion criteria in [Section 9.3.2](#) will not be eligible to receive study drug during the Core Study. Subjects who do not meet all of the inclusion criteria or who meet any of the exclusion criteria provided in [Appendix 6](#) will not be eligible to enter the OLE Phase. (revised per Amendment 07)

9.3.1 Inclusion Criteria

Subjects must meet all of the following criteria to be included in this study:

1. Meets the core clinical research criteria of the NIA-AA for MCI due to AD ([Albert, et al., 2011](#)) or AD dementia ([McKhann, et al., 2011](#)) and is "staged" or classified as either MCI or mild to moderate dementia and also complies with the following: (revised per Amendment 01)

Required at Screening Visit 1:

(revised per Amendment 02)

- a. Subjective Memory Complaint with evidence of concern about a decline in cognition from the subject, informant, or clinician's observation
 - b. Cognitive impairment of at least 1 SD from age adjusted norms in delayed recall on the ISLT. Alternatively, cognitive impairment of at least 0.5 SD from age-adjusted norms in delayed recall on the ISLT plus impairment of at least 1 SD from age-adjusted norms in at least 1 other computerized learning and memory test (ISLT immediate recall, or 1 of the learning and memory components of the CBB). (revised per Amendment 02)
 - c. FAQ ≤ 24 (revised per Amendment 01)
 - d. MMSE ≥ 16 (revised per Amendment 01)
2. Amyloid positive PET image based on centralized PET scan reading; an historical amyloid positive PET scan may be used if conducted within the previous 12 months and provided that the scan and result are considered acceptable by the central PET reading group (revised per Amendment 02)
 3. Male or female, age 50 to 85 years, inclusive at time of consent
 4. Must have an identified caregiver or informant who is willing and able to provide follow-up information on the subject throughout the course of the study. This person must, in the opinion of the investigator, spend sufficient time with the subject on a regular basis such that the caregiver or informant can reliably fulfill the study requirements and must provide separate written consent. The caregiver or informant need not be living in the same residence as the subject. If the caregiver or informant is not residing with the subject, the investigator has to be satisfied that the subject can contact the caregiver or informant readily during the times when the caregiver or informant is not with the subject. If in doubt about whether a subject's care arrangements are suitable for inclusion, the investigator should discuss this with the medical monitor. At visits where the CDR or FAQ are conducted, caregivers or informants need to either attend the visit in person along with the subject or be able to be contacted by telephone at the time of the visit. The investigator will determine whether attendance in person is required or whether telephone contact will be suitable and will base this determination upon the functional ability of the subject among other factors.
 5. If receiving acetylcholinesterase inhibitors (AChEIs) or memantine, must have been on a stable dose for at least 12 weeks before the Baseline cognitive assessments at Visit 2, with no plans for dose adjustment in the foreseeable future. Treatment-naïve subjects can be entered into the study but there should be no plans to initiate treatment with AChEIs or memantine at the time of entry into the study.
 6. Must have been on stable doses of all other permitted chronically used concomitant medications (ie, not related to their cognitive decline) for at least 4 weeks before randomization

9.3.2 Exclusion Criteria

Subjects who meet any of the following criteria will be excluded from this study:

1. Any neurological condition that may be contributing to cognitive impairment above and beyond that caused by the subject's AD pathology, including any co-morbidities detected by neurological examination or MRI
2. Modified Hachinski Ischemic Scale >4
3. History of transient ischemic attacks or stroke within 12 months of Screening
4. A history of epilepsy. Subjects with a history of seizures (not including a history of simple febrile seizures in childhood) within 10 years of Screening. Subjects with disturbance likely to be due to seizures within 5 years of Screening.
5. Significant pathological findings on the brain MRI at Screening, including but not limited to: more than 4 microhemorrhages (defined as 10 mm or less at the greatest diameter), any microhemorrhage which is symptomatic, a single macrohemorrhage greater than 10 mm at greatest diameter, an area of superficial siderosis, evidence of vasogenic edema, greater than 3 lacunar infarcts or a single infarct >2 cubic centimeters involving a major vascular territory, evidence of severe microangiopathy, evidence of cerebral contusion, encephalomalacia, aneurysms, vascular malformations, infective lesions or space-occupying lesions (however, lesions diagnosed as arachnoid cysts and <1cm in diameter at their greatest diameter need not be exclusionary) or brain tumors (eg, meningioma). (revised per Amendment 01)
6. Any psychiatric diagnosis or symptoms, (eg, hallucinations, major depression, or delusions) that could, in the opinion of the investigator, confound the MCI/Prodromal or mild to moderate AD diagnosis or could interfere with study assessments or procedures (revised per Amendments 01 and 02)
7. A score of ≥ 8 on the 15-item Geriatric Depression Scale (GDS) at Screening
8. Abnormally low serum vitamin B12 (<LLN) levels for the testing laboratory (if subject is taking vitamin B12 injections, level should be at or above the LLN for the testing laboratory) at Screening
9. Thyroid stimulating hormone above the normal range. Other tests of thyroid function with results outside the normal range should only be exclusionary if they are considered clinically significant by the investigator. This applies to all subjects regardless of whether or not they are taking thyroid supplements.
10. Subjects with hepatic impairment, with total bilirubin greater than $1.5 \times$ upper limit of normal (ULN) or International Normalized Ratio (INR) greater than 1.7 at Screening or Baseline. Subjects with Gilbert's syndrome need not be excluded.
11. Any contraindications to MRI or PET scanning, including cardiac pacemaker/ defibrillator or ferromagnetic metal implants (eg, in skull; cardiac devices other than those approved as safe for use in MRI scanners). Subjects who require sedation for MRI or PET scanning as per local guidelines need not be excluded.
12. Any contraindications to LP for CSF sampling (eg, lower spinal malformation on physical examination, local spinal infection or other abnormality, including but not

- limited to obesity). Only applicable to subjects consenting to CSF sample collection (revised per Amendment 02)
13. Severe visual or hearing impairment that would prevent the subject from performing psychometric tests accurately
 14. History of Ig deficiency or other immunodeficiency disorders (including subjects known to be human immunodeficiency virus positive)
 15. Subjects with chronic viral hepatitis
 16. A history of tuberculosis (TB). Subjects with no history of TB will be tested for previous TB exposure (eg, positive tuberculin skin test, interferon gamma release assay or other locally accepted tests) and a positive test will be exclusionary.
 17. A history of ophthalmic shingles
 18. A history of ocular herpes simplex virus (HSV) infection
 19. Any live vaccine in the 3 months before randomization.
 20. Any active infection within the last 4 weeks prior to randomization. For such cases, the timing of randomization can be extended (up to 4 weeks) to allow the infection to resolve; psychometric tests (eg, MMSE, CDR) and safety laboratory tests conducted at Visit 2 must be repeated. (revised per Amendment 02)
 21. Any chronic inflammatory disease that is not adequately controlled or that requires systemic or ocular immunosuppressive or immunomodulatory therapy. Subjects with:
 - a. Seasonal or perennial allergic rhinitis, asthma or chronic obstructive pulmonary disease where the condition is considered to be stable and adequately controlled by inhaled steroids need not be excluded.
 - b. Hashimoto's thyroiditis but who are stable on thyroid replacement therapy and not on systemic immunosuppressive therapy need not be excluded.
 - c. Cutaneous manifestations of immunological disease that do not require systemic immunosuppressive therapy or systemic immunomodulatory therapy need not be excluded (topical steroid treatment is permitted).
 22. CD4 (T helper cells), CD8 (cytotoxic T cells), or CD19 (B cells) absolute counts below population-adjusted LLN at Screening or Baseline and confirmed by a repeat test conducted 1 week after the initial test. The population-adjusted LLN for CD4 (T helper cells), CD8 (cytotoxic T cells), and CD19 (B cells) absolute counts are 396, 157, and 74 cells/ μ L respectively. See [Appendix 5](#). (revised per Amendment 02)
 23. Ig (IgG, IgA, or IgM) levels below the LLN at Screening or Baseline, unless both the Investigator and the Medical Monitor agree that the finding is not clinically significant. The assessment of clinical significance will include, but not be limited to, evidence of clinical immunodeficiency. The discussion with the Medical Monitor should include a detailed review of medical history of infections, clinical and laboratory findings. (revised per Amendment 01)
 24. Clinically significant deviation from normal in physical examination, vital signs, or clinically laboratory tests at Screening or Baseline

25. A prolonged QT/ corrected QT interval (QTc) interval (QTc >450 msec) at Screening or Baseline as demonstrated by average QTc interval from triplicate ECGs. A history of risk factors for torsade de pointes (eg, heart failure, hypokalemia, family history of long QT Syndrome) or the use of concomitant medications that prolong the QT/QTc interval.
26. Any other abnormality of the ECG at Screening or Baseline (including QRS >110 msec, abnormal electrical axis, PR interval >220 msec and conduction abnormalities) considered clinically significant by the investigator
27. Left bundle branch block at Screening or Baseline
28. Persistent heart rate <50 or >100 beats per minute (bpm) at Screening or Baseline
29. Persistent systolic blood pressure (BP) >165 mmHg or <90 mmHg and diastolic BP >100 mmHg or <60 mmHg at Screening
30. History of cardiac arrhythmias. Subjects with other heart diseases (eg, ischemic heart disease, clinically significant valvular heart disease) that are not stably and adequately controlled, or uncompensated heart failure (New York Heart Association Class III and Class IV)
31. Type 1 or Type 2 diabetes mellitus that is not well controlled
32. Malignant neoplasms within 5 years before Screening (except for basal or squamous cell carcinoma in situ of the skin, or localized prostate cancer that did not require systemic therapy; these do not exclude the subject). Subjects who had malignant neoplasms but who have had at least 5 years of documented evidence of no active disease before Screening need not be excluded.
33. Medical conditions (eg, cardiac, respiratory, gastrointestinal, renal disease) that are not stably controlled, or which, in the opinion of the investigator(s), could affect the subject's safety or interfere with the study assessments
34. Hypopigmentation conditions (eg, albinism and vitiligo). Diagnosis of an underlying disease causing hypopigmentation is not necessary for exclusion if the clinical presentation is consistent with such a condition. Hypopigmentation associated with scarring need not be exclusionary. (revised per Amendment 02)
35. Known or suspected history of drug or alcohol dependency or abuse within 2 years before Screening, current use of recreational drugs or a positive urine drug test at Screening. Subjects who test positive in the urine drug screen need not be excluded if in the clinical opinion of the investigator, this is due to the subject taking prior/concomitant medications for a medical condition that is not exclusionary and not due to drug abuse.
36. Has a "yes" answer to the C-SSRS suicidal ideation questions 4 or 5, or any suicidal behavior assessment within 6 months before Screening, at Screening, or at the Baseline Visit; or has been hospitalized or treated for suicidal behavior in the past 5 years before Screening
37. Violations of the medical restrictions as specified in the Concomitant Medications section of the protocol
38. Planned surgery that requires general, spinal, or epidural anesthesia that would take place

during the study. Planned surgery, which requires only local anesthesia and which can be undertaken as a day case without inpatient stay postoperatively, need not result in exclusion if in the opinion of the principal investigator this operation does not interfere with study procedures and subject safety.

39. Participation in any other interventional clinical study related to cognitive impairment within 6 months before Screening unless it can be documented that the subject was in a placebo treatment arm
40. Currently enrolled in another clinical study or used any investigational drug or device within 60 days or 5 half-lives of the investigational medication (whichever is longer) preceding informed consent
41. Hypersensitivity to the study drug or any of the excipients or to other BACE inhibitors, or to the PET tracer, or components of its formulation
42. Females who are lactating or pregnant (as documented by a positive beta-human chorionic gonadotropin [β -hCG] or human chorionic gonadotropin [hCG] test with a minimum sensitivity of 25 IU/L or equivalent units of β -hCG or hCG) at Screening or Baseline. A separate baseline assessment is required if a negative screening pregnancy test was obtained more than 72 hours before the first dose of study drug.
43. Females of childbearing potential who:
 - Had unprotected sexual intercourse within 30 days before study entry or who do not agree to use a highly effective method of contraception (eg, total abstinence, an intrauterine device, a double-barrier method [such as condom plus diaphragm with spermicide], a contraceptive implant, an oral contraceptive, or have a vasectomized partner with confirmed azoospermia) throughout the entire study treatment period or for 28 days after study drug discontinuation.
 - Are currently abstinent, and do not agree to use a double-barrier method (as described above) or refrain from sexually active during the study treatment period or for 28 days after study drug discontinuation.
 - Are using hormonal contraceptives but are not on a stable dose of the same hormonal contraceptive product for at least 4 weeks before dosing or who do not agree to use the same contraceptive during the study treatment period or for 28 days after study drug discontinuation.
 - (NOTE: All females will be considered to be of childbearing potential unless they are postmenopausal [amenorrheic for at least 12 consecutive months, in the appropriate age group, and without other known or suspected cause] or have been sterilized surgically [ie, bilateral tubal ligation, total hysterectomy, or bilateral oophorectomy, all with surgery at least 1 month before dosing]). (revised per Amendment 04)

